National Institutes of Health (NIH)-funded investigators and clinical trial site staff who are responsible for the conduct, management, or oversight of NIH-funded clinical trials have completed Human Subjects Protection and ICH GCP Training.

The protocol, informed consent form(s), recruitment materials, and all participant materials will be submitted to the IRB for review and approval. Approval of both the protocol and the consent form(s) must be obtained before any participant is consented. Any amendment to the protocol will require review and approval by the IRB before the changes are implemented to the study. All changes to the consent form(s) will be IRB approved; a determination will be made regarding whether a new consent needs to be obtained from participants who provided consent, using a previously approved consent form.

1 Protocol Summary

1.1 Synopsis

Title: Feasibility of tight control versus usual postpartum care following hypertensive disorders of pregnancy: a randomized controlled trial

Study Description:

Objectives:

- Primary Objective: To assess the feasibility of conducting a randomized controlled trial of tight blood pressure control (<135/85 mmHg on home blood pressure monitoring) vs. standard of care (<150/100 mmHg on home blood pressure monitoring) in postpartum individuals following a hypertensive disorder of pregnancy (HDP).
- Secondary Objectives: To assess the effect of tight blood pressure control on longer-term blood pressure control and postpartum care utilization to inform sample size for a subsequent large-scale randomized trial

Endpoints:	Primary Endpoint:	Proportions of individuals who are eligible, enroll, and remain in the study through 6 weeks postpartum (Target: >40% enrollment, >80% retention)
	Secondary Endpoints:	Mean arterial blood pressure, systolic blood pressure, and diastolic blood pressure at 6 weeks and 6 months postpartum at a research study visit. Proportion with stage 1 or greater hypertension at each study visit. Mean home blood pressures throughout first six weeks postpartum. Care utilization including postpartum emergency room visits, hospital readmissions, and outpatient office visits.

Study Population:

Phase:	3
Description of Sites/Facilities Enrolling Participants:	Single-center, tertiary care center
Description of Study Intervention:	Tight blood pressure control defined as goal home blood pressure <135/85 via remote blood pressure monitoring for 6 weeks postpartum
Study Duration:	6 months

Participant 6 months
Duration:

1.2 Schema

1.3 Schedule of Activities (SoA)

2 Introduction

2.1 Study Rationale

There are inconsistent clinical recommendations for management of postpartum hypertension. There is overwhelming evidence of benefit of lower BP targets in a non-pregnant population and in individuals with chronic hypertension in pregnancy.^{22,23} Specifically for non-pregnant individuals, the American College of Cardiology (ACC) recommended BP threshold for initiation of an antihypertensive medication is 140/90 mmHg and even lower, 130/80 mmHg, for individuals at high risk for CVD. Recently, the Chronic Hypertension and Pregnancy (CHAP) trial found benefit in targeting a BP threshold of 140/90 mmHg for initiation of medications during pregnancy for individuals with chronic hypertension.²² Despite this, ACOG continues to recommend a threshold of 150/100 mmHg for initiation of anti-hypertensive medications in the postpartum period.⁹ This approach fails to consider the anticipated exacerbation of hypertension and is likely a contributor to hypertension-related maternal morbidity and mortality in the postpartum period.²⁴ Despite the inconsistent management recommendations, professional societies (including ACOG, ACC and Society for Maternal Fetal Medicine) recognize the public health significance and the need for a well-designed trial to evaluate the benefits and harms of tighter blood pressure control in the postpartum period.^{9,27,28}

2.2 Background

Rising rates of cardiovascular disease (CVD) in women make it a major public health concern.¹ Despite this, women remain underrepresented in cardiovascular clinical trials relative to their percentage of the population and disease burden.^{2–4} The urgency of these trends is amplified by the fact that chronic hypertension is a condition that increases more rapidly during the reproductive years with worse morbidity in females compared with males.⁵ There are meaningful, sex-based differences in symptomatology and clinical outcomes of CVD in women.

Compared to men, women are diagnosed later, are less likely to receive guideline-concordant care and overall quality of care is significantly lower.^{6,7} Collectively, these findings translate to stagnant mortality rates from CVD in women, particularly young women, and emphasize the importance of approaches that are centered on female-specific risk factors and target primary prevention.^{6,8}

Women with hypertensive disorders of pregnancy progress rapidly to chronic hypertension in the first few years after delivery. The trajectory of blood pressure from HDP to chronic hypertension remains understudied and poorly understood. The prior clinical approach in obstetrics was that the pathogenesis of preeclampsia is resolved with delivery. This hands-off approach to management has likely contributed to the increasing maternal morbidity and mortality seen in the postpartum period. In the largest United States contemporary cohort of individuals (nuMoM2b/Heart Health Study), 37% of women with a hypertensive disorder of pregnancy developed chronic hypertension by 3 years postpartum.¹⁰ In our pilot work of individuals with a hypertensive disorder of pregnancy and pre-pregnancy obesity, 58% developed stage 1 hypertension or greater by one-year after delivery. There is compelling evidence that the preponderance of HDP-associated CVD risk is linked to progression to chronic hypertension following pregnancy, yet the recovery of blood pressure and transition to chronic hypertension remains understudied.^{10,21} Prevention in this population should target the critical time period of the first year after delivery.^{16,17}

Recent evidence suggests the immediate postpartum period is a critical time for CV remodeling, with implications for long-term maternal health. Small RCTs have demonstrated that improved management of hypertension immediately postpartum leads to longer-term BP benefits.²⁹ In the SNAP-HT trial, done in the United Kingdom, self-managed of BP with home monitoring and tight BP control led to improved diastolic BP at 6 months postpartum that was sustained through 3-4 years after delivery in n=62 women. A similar proportion of women were on anti-hypertensive medications at 6 months postpartum across both arms, but tighter BP control during the critical immediate postpartum period led to lower BP long-term (-4.5 mmHg office diastolic BP at 6 months and -6.8 mmHg ambulatory diastolic BP at 3-4 years). Similarly, in our data, the proportion of BPs that are <140/90mmHg in the first six-weeks postpartum is associated with a lower risk of hypertension at one-year postpartum and lower relative wall thickness and LV remodeling (see preliminary data). We hypothesize that this benefit is secondary to improved CV remodeling during this critical period that results in long-term BP benefit that is sustained beyond the intervention period. In this application, we will directly test this hypothesis in an adequately-powered trial designed to assess the impact of tight postpartum BP control on long-term BP and cardiac remodeling.

Successful execution of a postpartum intervention trial requires established collaborations between high-risk obstetricians and cardiologists and can leverage existing, effective

infrastructure for home monitoring and retention postpartum. This line of research is distinctly at the intersection of high-risk obstetrics and cardiology. While trials conducted during pregnancy could be executed entirely within the context of prenatal care, our proposed study extends to 1 year postpartum and cannot be implemented fully within the care structure of solely an obstetrics or cardiology practice. Rather, to effectively study this critical question requires the collaborative infrastructure that we have successfully established at our institution. We have developed and enrolled over 9,000 women with HDP into a clinical postpartum remote hypertension management program, who have contributed >150,000 BPs in the first 6 weeks postpartum. We demonstrate high adherence, patient satisfaction, and a reduction in hospital readmission among our population (see preliminary data).^{25,32,33} We have recently expanded this remote BP monitoring 6 week program to 1 year postpartum, housed within our highly successful multi-disciplinary postpartum hypertension clinic. Despite our program's success, at the conclusion, 30% of women still require anti-hypertensive medications, and at 1 year postpartum, 50% remain hypertensive. These peripartum BP trends likely contribute to an "unexplained epidemic" of increased CVD among young women, and suggest that further interventions may be necessary to improve hypertension and CV-related maternal morbidity following a HDP.

Cardiovascular disease (CVD) is the leading cause of death in women worldwide, and despite declines in all other age groups, mortality rates attributed to CVD are increasing in women of childbearing age. Hypertensive disorders of pregnancy (HDP), including preeclampsia and gestational hypertension, are female-specific conditions that are well-established risk factors for CVD across diverse patient populations. There is compelling evidence that the preponderance of HDP-associated CVD risk is linked to progression to chronic hypertension following pregnancy. The urgency of these trends is amplified by the fact that chronic hypertension is a condition that increases more rapidly during the reproductive years with worse morbidity in females compared with males. Understanding and mitigating progression to chronic hypertension in the postpartum period after a HDP may prevent CVD, a critical yet under-studied period of risk and an important opportunity for intervention to prevent chronic disease in women.

Hundreds of studies in non-pregnant or postpartum adults demonstrate that lower blood pressure reduces CV-related morbidity and mortality. However, the thresholds for postpartum anti-hypertensive medication initiation remains at 150/100 without change in over 30 years. HDP carry a high risk of persistent postpartum hypertension, with 20-30% still requiring antihypertensive medications at 6 weeks after delivery and up to 50% with chronic hypertension at one-year postpartum. While recent data from a multi-center randomized controlled trial (RCT) demonstrate that tighter BP control during pregnancy in individuals with mild chronic hypertension improves maternal and fetal outcomes, postpartum BP management is unstudied.

The current blood pressure thresholds for anti-hypertensive medication initiation for all adults, except pregnant and postpartum individuals is 140/90 mmHg in the clinic or 135/85 mmHg at

home. The American College of Obstetricians and Gynecologists recommends postpartum initiation of medication for persistent BP $\geq 150/100$ mmHg, a much higher threshold for treatment than in non-pregnant or postpartum adults. These recommendations do not account for the expected exacerbation of hypertension that occurs at days 4-7 postpartum, which is associated with an increase in postpartum hospital readmission, severe hypertension and maternal morbidity. Small trials in the United Kingdom have shown that tight BP control during a critical period postpartum improves BP years postpartum. We have compelling observational data that higher BP ($>140/90$ mmHg) in the first six weeks postpartum is associated with an increased risk of concentric left ventricular remodeling and development of chronic hypertension at one to two years postpartum. We have developed and implemented a clinical postpartum remote hypertension management program that has enrolled over 9000 of individuals with HDP who deliver in our hospital system since 2018. We plan to leverage this robust, well-established infrastructure to conduct an urgently needed randomized trial to generate definitive evidence on appropriate BP treatment thresholds in the postpartum period following a hypertensive disorder of pregnancy to prevent chronic hypertension and other cardiovascular sequelae.

The overall objective of this study is to assess the feasibility of conducting a single-site RCT within our remote BP management program of tight BP control versus usual care in the immediate postpartum period through 6 months in individuals with a HDP.

2.3 Risk/Benefit Assessment

2.3.1 Known Potential Risks

- Symptomatic hypotension
- Possible decrease in breastmilk supply impacting breastfeeding continuation

2.3.2 Known Potential Benefits

- Possible lower rates of progression to chronic hypertension
- Possible reduction in healthcare utilization postpartum

2.3.3 Assessment of Potential Risks and Benefits

3 Objectives and Endpoints

OBJECTIVES	ENDPOINTS	JUSTIFICATION FOR ENDPOINTS
Primary		
	
Is a randomized controlled trial of tight blood pressure control (<135/85 mmHg on home blood pressure monitoring) vs. standard of care (<150/100 mmHg on home blood pressure monitoring) in postpartum individuals following a hypertensive disorder of pregnancy (HDP) feasible?
 
We hypothesize that average enrollment will represent 10 participants per month, greater than 80% of enrolled participants will undergo randomization, and six-month retention will represent greater than 80% of randomized patients.
	
The outcome measures will determine whether a large-scale randomized controlled trial is feasible at our institution.

Secondary		
	
Does randomization to tight blood pressure control (<135/85 mmHg on home blood pressure monitoring) following a hypertensive disorder of pregnancy result in lower mean arterial pressure (MAP) at 6 weeks and 6 months postpartum to inform the sample size for a large-scale randomized trial?
 
We hypothesize that among women randomized to tight blood pressure control, there will be lower mean arterial blood pressures (MAP) at 6 months postpartum and can ascertain the sample size for a large-scale randomized trial accordingly.
 
Does randomization to tight blood pressure control (<135/85 mmHg on home blood pressure monitoring) following a hypertensive disorder of pregnancy result in lower diastolic
	
Mean arterial pressure (MAP): Importantly, MAP accounts for both systolic and diastolic BP, and weights diastolic BP more strongly. While most hypertension trials in older adults employ systolic BP as the primary outcome, our preliminary data supports the importance of isolated diastolic hypertension in young women, particularly following a hypertensive disorder of pregnancy.
 
Systolic blood pressure and diastolic blood pressure are surrogate values for diagnosis of elevated blood pressure at 6 weeks and 6 months postpartum.

OBJECTIVES	ENDPOINTS	JUSTIFICATION FOR ENDPOINTS
	
blood pressure, systolic blood pressure at 6 weeks and 6 months postpartum to inform the sample size for a large-scale randomized trial?
 
We hypothesize that among women randomized to tight blood pressure control, there will be lower systolic blood pressure, diastolic blood pressure at 6 weeks and 6 months postpartum and can ascertain the sample size for a large-scale randomized trial accordingly.
	
Tertiary/Exploratory		
	
Does randomization to tight blood pressure control (<135/85 mmHg on home blood pressure monitoring) following a hypertensive disorder of pregnancy result in changes in lower care utilization through analysis of emergency room visits, hospital readmissions, and outpatient office visits for the first 6 months postpartum?
 
We hypothesize that among women randomized to tight blood pressure control, there will be a lower rate of postpartum care utilization.
	
Postpartum care utilization comprises use of health care resources which can be ascertained by rates of emergency room visits, hospital readmissions, and outpatient office visits within our hospital system.

[figure not shown]
4 Study Design

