5.3 Strategies for Recruitment and Retention

Recruitment: We will recruit 60 individuals with preeclampsia or gestational hypertension from the MWH postpartum units, using recruitment methods effectively employed by our team previously. There are approximately 100 eligible individuals per month (~1200 per year).

We plan to recruit women from the post-delivery unit with the appropriate diagnoses. Upon review of a potential subject's chart to determine eligibility, the study coordinator will flag the chart for potential eligibility. The potential participant will first be approached by the study physician or a member of the clinical care team directly caring for her to ask about her willingness to be approached for participation in a research study. If the potential participant indicated willingness to be approached, then the research team will be contacted and the potential subject will be screened regarding enrollment.

Retention: Participants will receive monetary compensation which will be distributed amongst their study visits. We propose monetary compensation of \$125 total with \$25 distributed at enrollment, \$25 distributed at the first study visit, and \$25 distributed at the second study visit and \$50 at the final study visit.

Randomization and blinding: We will randomize consented participants into two arms: tight BP control (<135/85 mmHg) vs. usual care in 1:1 at the individual level. A randomization sequence using permuted block randomization with randomly varying block sizes will be generated by RedCap. This will be a pragmatic, non-masked trial. At randomization, treating physicians will be notified of their patient's participation and randomization group.

6 Study Intervention

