8.1 Efficacy Assessments

Feasibility outcomes: As listed in Table, will include enrollment, randomization, retention.

Blood pressure measurement: Mean arterial pressure (mmHg) at six weeks and six months postpartum will be assessed at a remote research study visit. MAP is defined as the average BP during one cardiac cycle and will be calculated

as $MAP = SBP + 2(DBP)/3$. BP will be measured in all women in a standardized manner by trained research staff using the same validated device as at the enrollment visit. Due to diurnal variations in BP, we will attempt to schedule all study visits between 8-10am consistent with clinical guidelines. If this cannot be performed due to participant scheduling limitations, we will ensure that BP is measured at a consistent time of the day across all visits. Following a 5-minute rest, BP will be measured in triplicate on the non-dominant arm with one-minute intervals using an appropriately sized cuff. These measures will be directly observed by research study staff.

Table. Feasibility outcomes		
Feasibility outcome	Descriptive statistic	Feasibility target
Identification of participants	mean, SD, 95% CI	Review 50 medical records per month to assess for eligibility
Screening	mean, SD, 95% CI	Average screening rate of 8-10 participants/month
Enrollment	mean, SD, 95% CI	Average enrollment rate of 4-5 participants/month
Randomization	n, %, 95% CI	>80% of enrolled participants
Retention to 6 months postpartum	n, %, 95% CI	>80% of randomized participants
Study measures consistency	n, %, 95% CI	>90% of randomized participants
Acceptability	n, %, 95% CI	>80% of randomized participants based on survey questionnaires

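### The primary feasibility criteria conflict on enrollment rate and retention time point, and the >40% enrollment target has no denominator, so the same data could be labelled feasible or not feasible

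*Combined protocol and SAP*

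**What the plan says.** **Enrollment.** The primary hypothesis in Section 3 (Objectives and Endpoints) is that "average enrollment will represent 10 participants per month". The feasibility table in Section 8.1 lists "Average enrollment rate of 4-5 participants/month", next to "Average screening rate of 8-10 participants/month" and "Review 50 medical records per month to assess for eligibility". The primary endpoint in the Synopsis (1.1) gives a proportion instead: "Target: >40% enrollment, >80% retention". It does not say what the 40% is a percentage of. Section 5.3 puts the eligible pool at about 100 women per month.

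**Retention.** The Synopsis attaches its retention target to remaining in the study through 6 weeks. Section 3 states that "six-month retention will represent greater than 80% of randomized patients", and the Section 8.1 table also sets >80% of randomized participants at 6 months. Section 4.1 assesses retention to six weeks and then, further, to 6 months, with no threshold at either. Section 9.4.2 reports retention at each outcome assessment, again with no threshold or priority.

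**Precedence.** No section says which target governs, or whether an estimate or a confidence limit is to be compared with it.

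**The concern.** Section 3 says that these outcome measures will decide whether a large trial is feasible at the institution. A pilot of this kind is useful for that decision only if the criteria are fixed beforehand. Here one metric, women enrolled per month, has two values, and one threshold, >80% retained, sits on two dates. A third target cannot be evaluated until someone picks a denominator. Whoever writes the report could make these choices after seeing the data. A 2- to 2.5-fold difference in expected accrual would also carry straight into planning the larger trial.

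**Working it through.** **1. The plan's own figures.** Section 9.2 states a within-arm 95% margin of error of at most 0.18 with 30 per arm. The worst case is p = 0.5: 1.96 × √(0.5 × 0.5 / 30) = 0.179, which reproduces it. The power statement (24 per arm, SD 8, difference 5 mmHg, two-sided alpha 0.20) gives 81.2% by the normal approximation and 80.6% by the t distribution, against the stated 80%. Neither figure is affected by this point.

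**2. Enrollment targets on a common scale.** The inputs are 8-10 screened and 50 records reviewed per month (Section 8.1), about 100 eligible per month (Section 5.3) and 60 participants (Sections 5.3 and 9.2).

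| Target | Enrolled per month | Share of 8-10 screened | Share of 50 records | Share of about 100 eligible | Months to enroll 60 |
|---|---|---|---|---|---|
| Section 3 | 10 | 10/10 to 10/8 = 100-125% | 20% | 10% | 60/10 = 6 |
| Section 8.1 table | 4-5 | 4/10 to 5/8 = 40-62.5% | 8-10% | 4-5% | 60/5 to 60/4 = 12-15 |
| Synopsis, if of screened | more than 3.2-4 | >40% | more than 6.4-8% | more than 3.2-4% | under 15-18.75 |
| Synopsis, if of eligible | more than 40 | more than 400-500% | more than 80% | >40% | under 1.5 |

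Ten per month is compatible with the table's screening target only at the limit of 10 screened and all 10 enrolled. Five per month meets the table and is half the Section 3 figure. It passes >40% if the denominator is women screened (50-62.5%) and fails if it is eligible women (5%). Four enrolled from 10 screened is exactly 40%, so it meets the table's rate and misses a strict >40%.

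**3. Retention.** With 60 randomized, 48/60 is exactly 80%, so >80% needs at least 49. For illustration (assumed counts), 54/60 = 90% at 6 weeks meets the Synopsis target, and 45/60 = 75% at 6 months fails Section 3 and the table. The binomial probability of at least 49 of 60 depends on true retention (assumed values):

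- 90%: 98.5%
- 85%: 81.9%
- 80%: 44.9%
- 75%: 14.8%

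If retention falls between 6 weeks and 6 months, the choice of date can decide the result.

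**4. Estimate or confidence limit.** For 54/60 the exact 95% interval is 79.5% to 96.2%. The estimate clears 80% and the lower limit does not, so this choice can also change the label.

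**5. Study duration.** The Synopsis gives 6 months, which equals one participant's follow-up. Accrual plus 6 months of follow-up for the last participant gives:

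- If every enrolled woman is randomized: 6 + 6 = 12 months at 10 per month; 12 + 6 = 18 to 15 + 6 = 21 months at 4-5 per month.
- If 80% are randomized (the threshold in Section 3 and the table): 60/0.8 = 75 must enroll. That takes 7.5 + 6 = 13.5 months at 10 per month, and 15 + 6 = 21 to 18.75 + 6 = 24.75 months at 4-5 per month.

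**The case against.** The best defence is that the Section 8.1 table already governs. It has the only column of feasibility targets, and Section 8.1 defines the feasibility outcomes by reference to it, whereas the 10 per month in Section 3 is a hypothesis. That is arguable, but it does not settle the matter. The Synopsis names a primary endpoint with its own targets and a different retention date, Section 3 places its figures under the primary objective, and nothing gives the table precedence.

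Several other defences stand and limit the point:

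- A reader might infer three mutually conflicting enrollment targets. The documents do not support that. The >40% is a proportion, and against women screened it fits 4-5 per month apart from the boundary case. Its defect is the missing denominator.
- A reader might infer that the criteria cannot all be met. If dropout only accumulates, >80% at 6 months implies >80% at 6 weeks; if the rates are minimums, 10 per month also satisfies 4-5. The criteria differ in strictness.
- Measuring retention at both visits is legitimate, and Section 4.1 sets no 80% threshold. Only the primary label is in dispute.
- Ten per month is only 10% of the eligible pool. It is out of line with the screening target, not with the hospital's volume.
- Section 9.4.1 makes estimation the focus, with 95% intervals overall and by arm, so the underlying figures would be reported under any reading.

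**Conclusion.** The point holds for the pass/fail criteria. One enrollment metric has two values that differ by a factor of 2 to 2.5, the primary >80% retention target is tied to two different dates, and the >40% target cannot be evaluated as written. With 5 enrolled per month, 90% retained at 6 weeks and 75% at 6 months, the trial could be reported as feasible or not feasible. Those values are illustrative; the conflict between the targets does not depend on them.

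It would go too far to conclude that the trial cannot answer its question: the rates and retention proportions would still be estimated, and the sample-size figures reproduce. What is missing is a single rule, fixed in advance, for turning the estimates into a verdict.

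The Study Duration is a secondary, administrative point that does not bear on the verdict. The plan's own rates imply about 12 months at 10 per month (13.5 if 80% of enrolled women are randomized), or about 18 to 25 months at 4-5 per month.

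**What to change.** Put one table of primary feasibility criteria in the protocol and use it unchanged in the Synopsis and Sections 3, 4.1, 8.1 and 9.4.2.

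- **Enrollment rate:** keep one value. The 4-5 per month fits the current screening target. If 10 per month is kept, raise the screening target to match.
- **Enrollment proportion:** state a single denominator for the 40%, for example eligible women screened by the research team. Section 5.3 treats the care team's approach and the research team's screening as separate steps, so name one. Align it with the rate target: use ≥40%, or adjust the rate, because 4 of 10 is exactly 40%.
- **Retention:** label one time point primary, with all randomized participants as the denominator, and the other supportive. Six months would match Section 3 and the table. Six weeks would be equally clear if labelled everywhere.
- **Decision rule:** state whether the point estimate or a confidence limit must clear each target.
- **Study Duration:** restate it from the chosen enrollment rate and the assumed proportion randomized.

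The cost is protocol wording, with no added participants or visits. The one downside is that a 6-month primary retention criterion is harder to meet than a 6-week one.

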Secondary outcomes are systolic and diastolic BP, and chronic hypertension at 1-year postpartum (stage 1 or stage 2) derived from office BP in women randomized to tight control compared to women to receiving usual care. We will also compare the use of anti-hypertensive agents across the study period, quantitatively assessed using the therapeutic intensity score [TIS], which is a summary measure that accounts for the number of medications and the relative doses received, which will be summarized across the study period and compared by randomization arm. As an exploratory analysis, we will quantitatively simulate BP based on confounding effects of anti-hypertensive medications using published metrics of the lowering effect of various anti-hypertensive agents. Finally, we will evaluate care utilization across study arms, including postpartum readmission and Emergency Room visits

Questionnaires: The participant will complete questionnaires about demographics, medical history, obstetric and gynecologic history, physical activity, mood, diet, breastfeeding, sleep, and overall health and support. At subsequent visits, the participant will also answer questions about the intervention.

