8.2 Safety and Other Assessments

Answering Questionnaires: There is a possibility of emotional discomfort associated with answering the questionnaire as some of the questions may be considered “personal” and answering them might be stressful or embarrassing. Participants may skip questions for which they feel uncomfortable.

Risks of the Tight Control Intervention Program: For some women, there may be a small but present risk of hypotension, meaning your blood pressure goes too low. If this occurs, it may cause symptoms such as dizziness, shortness of breath, palpitations, light-headedness, and/or falls. We advise women who are experiencing these symptoms to immediately contact their health-care provider and to avoid carrying their newborn due to risk of falls. Additionally, we will monitor rates of breastfeeding continuation given the theoretical risk for decreased milk supply.

9 Statistical Considerations

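### Emergency visits and readmissions are compared by arm without regard to cause, so visits for hypotension, a named risk with no endpoint, can be offset by averted hypertension visits and go unseen

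*Combined protocol and SAP*

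**What the plan says.** **The measure.** The synopsis lists as a secondary endpoint: "Care utilization including postpartum emergency room visits, hospital readmissions, and outpatient office visits". Section 3 places utilization under Tertiary/Exploratory and measures it by "rates of emergency room visits, hospital readmissions, and outpatient office visits within our hospital system". Section 8.1 says "we will evaluate care utilization across study arms, including postpartum readmission and Emergency Room visits", without naming office visits. None of these places records why a visit took place.

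**The direction.** Section 2.3.2 lists as a benefit "Possible reduction in healthcare utilization postpartum". The Section 3 hypothesis is directional: "We hypothesize that among women randomized to tight blood pressure control, there will be a lower rate of postpartum care utilization".

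**The harm.** Section 2.3.1 names "Symptomatic hypotension" as a known risk. Section 8.2 describes its symptoms, including falls, and says "We advise women who are experiencing these symptoms to immediately contact their health-care provider". The same section commits to monitoring breastfeeding continuation but makes no such commitment for hypotension. Section 9.4.4, Safety Analyses, is a heading with no text. Section 9.4.2 collects perceived harms as part of acceptability, and section 7.2 records the reason for any withdrawal.

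**The concern.** On the plan's own account, tight control can move visits in two directions. Section 2.2 links the blood pressure rise at days 4-7 to readmission and severe hypertension, so better control could avert some visits. Hypotension could add others, because symptomatic women are directed towards care. If reasons are not recorded, one emergency visit averted and one added leave the emergency-visit rate unchanged. Reporting emergency visits and readmissions separately does not help, because the offset happens within each type.

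The pilot could then report equal or lower utilization while hypotension visits gather in the tight arm. Section 9.2 says the pilot exists to collect information for planning a larger study, and visits for the main named harm, by arm, are part of what that study's safety plan would need. The feasibility conclusion is not affected.

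**Working it through.** **1. The plan's own figures.** The plan states no rate, sample size or power for utilization, so there is no utilization figure to reproduce. Section 9.2 gives 30 women per arm and a margin of error of at most 0.18. The check is 1.96 × √(0.25/30) = 0.179, which agrees. I use 30 per arm below.

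**2. Why the total can hide the cause.** For one visit type, let p_C be the risk of a hypertension visit in usual care, p_T the same risk under tight control, and p_H the risk of a hypotension visit under tight control. The expected difference in visits (tight minus usual) is 30 × (p_T + p_H − p_C). It is zero whenever p_H = p_C − p_T, however large p_H is.

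**3. How often this could happen.** All rates here are assumptions. Counts are independent binomials with n = 30: C for usual care, and T and H for the tight arm. Usual care has no hypotension visits, and visits for other reasons are left out. For each scenario I computed by exact summation:
- A = P(T + H ≤ C): the tight-arm total is no higher than usual care.
- B = P(T + H ≤ C and H ≥ 2): the same, with at least 2 hypotension visits in the tight arm.
- D = P(H ≥ 2) = 1 − (1 − p_H)^30 − 30 p_H (1 − p_H)^29.

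| p_C | p_T | p_H | Expected visits, usual vs tight | A | B | D | B/D |
|---|---|---|---|---|---|---|---|
| 13% | 3% | 10% | 3.9 vs 3.9 | 57.8% | 41.1% | 81.6% | 50% |
| 20% | 10% | 10% | 6.0 vs 6.0 | 56.5% | 41.1% | 81.6% | 50% |
| 13% | 5% | 5% | 3.9 vs 3.0 | 71.6% | 24.5% | 44.7% | 55% |
| 13% | 3% | 2% | 3.9 vs 1.5 | 91.2% | 8.8% | 12.1% | 73% |
| 13% | 3% | 1% | 3.9 vs 1.2 | 94.0% | 2.7% | 3.6% | 75% |

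B falls from 41% to 3% as p_H falls from 10% to 1%, mainly because two or more hypotension visits become rare (column D). Once they do occur, the total is still no higher than usual care in half to three quarters of cases (column B/D). In the first two rows the zero expected difference is an input, because p_H was set equal to p_C − p_T.

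**4. What a split by cause would show.** If 3 of 30 women in the tight arm and 0 of 30 in usual care had a hypotension visit, the exact (Clopper-Pearson) 95% intervals would be 2.1% to 26.5% and 0% to 11.6%. The upper limit for 0/30 is 1 − 0.025^(1/30) = 0.116. The chance of at least one affected woman among 30 is 1 − (1 − p)^30, which is 45%, 79% and 96% at p = 2%, 5% and 10%. The intervals are wide, but the harm would be visible by arm.

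**The case against.** **The documents do not show that hypotension generates these visits.** Section 8.2 calls the risk small and asks women to contact a provider, which could be a telephone call that no visit type counts. This stands. It is why the size is given as a range and why the low end is about 3%.

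**All-cause utilization is a legitimate outcome.** If the question is total use of health care in a pragmatic trial, setting added visits against averted ones is what is wanted. This also stands, so the all-cause rates and the hypothesis should stay. Limiting the hypothesis to hypertension-related visits might look like a natural remedy, but it would remove side-effect visits from the compared outcome and so favour tight control.

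**The consequence is small.** Section 3 makes utilization exploratory, although the synopsis calls it secondary. Section 9.4.1 puts estimation ahead of testing, and section 4.1 bases the later sample size on blood pressure. This stands and limits the weight of the point.

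**Harms are captured elsewhere.** Perceived harms enter acceptability (9.4.2) and withdrawal reasons are recorded (7.2). Neither gives a count of hypotension events by arm, so this answers the point only in part.

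**Two stronger readings go beyond the text.** A reader might infer that all visits are added into one composite. The plan names three visit types and speaks of rates for each; no sum is defined. A reader might also infer that titration adds office visits in the tight arm. Section 6.1.2 has titration in both arms, section 6.1.1 runs management through remote nurses, and no section says that titration needs an office visit.

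**Conclusion.** The point holds in a limited form. Emergency visits and readmissions are compared without regard to cause, fewer is the stated benefit, and a named harm that can lead to such visits has no endpoint and no planned analysis. Within a visit type, benefit and harm can offset each other unseen.

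The documents give no rates, so neither the size nor the occurrence of an offset can be established. The 3% to 41% range rests on hypotension visit rates of 1% to 10% in the tight arm and none in usual care, the hypertension visit rates in the table, and no visits for other reasons. It shows that masking is possible, not that it will happen. A reader might infer that the plan nets a known harm out of its results; the text supports only that it would not reveal such netting. This is a cheap improvement, not a threat to the feasibility objective.

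**What to change.** Keep the all-cause rates by visit type and the existing hypothesis. In sections 8.1 and 9.4.3, add that each emergency visit and readmission will also be classified from its recorded diagnosis as:
- (a) hypertension-related;
- (b) hypotension, fall or antihypertensive side effect; or
- (c) other.

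Fix the categories before data are reviewed and, where possible, have them coded without knowledge of arm. Report each category by arm with exact 95% CIs, and report category (b) under section 9.4.4 as safety.

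The cost is a few lines of protocol text and one code for each encounter already being ascertained in 60 women. The downside is small counts per category and some coding judgement in an unmasked trial. No treatment threshold or clinical rule changes.
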